2. STUDY OBJECTIVE

2.1. Primary Objective

To evaluate the effect of the addition of ibrutinib to rituximab on progression-free survival (PFS) assessed by an independent review committee (IRC) in subjects with WM. Efficacy evaluations will be based on the modified Consensus Response Criteria from the VIth International Workshop for WM (NCCN 2014).

2.2. Secondary Objective(s)

Efficacy

To compare the treatment arms in terms of the following:

- Overall Response Rate (ORR) assessed by IRC (\geq PR; according to the modified VIth IWWM [NCCN 2014] criteria).
- Hematological improvement measured by hemoglobin.
- Time to next treatment (TTnT).
- Overall survival (OS).

Safety

- To evaluate the safety and tolerability of ibrutinib when combined with rituximab therapy compared to rituximab in combination with placebo.

2.3. Exploratory Objectives

- Patient-reported outcomes (PRO) and disease-related symptoms according to FACT-An.
- Patient-reported outcomes (PROs) and disease-related symptoms according to Euro QoL 5 dimension questionnaire (EQ-5D-5L).
- Duration of response (DOR) according to IRC assessment.
- Clinical response rate (CRR) assessed by IRC (\geq MR; according to the modified VIth IWWM [NCCN 2014] criteria).
- Efficacy assessment by Investigator (\geq PR and \geq MR; according to the modified VIth IWWM [NCCN 2014] criteria).
- To determine the pharmacokinetics (PK) of ibrutinib in combination with rituximab in subjects with WM.
- Evaluation of medical resource utilization (MRU) (eg, requirements of plasmapheresis, transfusions and use of growth factors).
- Prognostic and predictive biomarkers and genetics relative to treatment outcomes.

Open-label Substudy Treatment Arm C

The objectives are to evaluate the efficacy and safety of open-label ibrutinib monotherapy in WM subjects who are considered refractory to the last prior rituximab-containing therapy (refer to [Section 4.2](#)). PFS, ORR, hematological improvement measured by hemoglobin, TTnT, FACT-An, OS and other efficacy parameters as well as safety analyses will be summarized descriptively for Arm C. No comparator analysis will be done with Arms A or B.

3. STUDY DESIGN

3.1. Overview of Study Design

This is a randomized, placebo-controlled, double-blind, Phase 3 study designed to evaluate whether treatment with ibrutinib in combination with rituximab will result in an improvement in PFS compared to placebo in combination with rituximab in subjects with WM. In addition, an open-label ibrutinib substudy is included to further investigate the safety and efficacy of ibrutinib monotherapy in subjects with WM who are considered refractory to the last prior rituximab-containing therapy (refer to [Section 4.2](#)).

The study duration is estimated to be 4 years with approximately 1.5 years of enrollment and 3 years of follow up. The end of study will occur approximately 3 years after the last subject is randomized, or the Sponsor terminates the study, whichever comes first.

Approximately 150 subjects will be randomized in a 1:1 ratio to receive ibrutinib and rituximab (Treatment Arm A) or placebo and rituximab (Treatment Arm B).

Up to 30 subjects will be enrolled in the open-label ibrutinib monotherapy substudy (Treatment Arm C).

The study will include a Screening Phase, Treatment Phase and a Follow-Up Phase.

The Screening Phase assessments will be performed within 30 days prior to study treatment and will begin on the day the subject signs informed consent. During the Screening Phase, the subjects' eligibility will be determined. Eligible subjects must have clinicopathological diagnosis of Waldenström's macroglobulinemia (WM) confirmed by central pathology review and in accordance with the consensus panel of the Second International Workshop on WM ([Owen 2003](#)). Subjects with previously treated WM must have documented relapsed/refractory disease from their most recent prior therapy according to the modified WM consensus criteria. Further, subjects must have symptomatic disease meeting at least 1 of the recommendations from the Second International Workshop on Waldenström's Macroglobulinemia for requiring treatment. Subjects who meet all the inclusion/exclusion criteria are eligible to enter the study.

The Treatment Phase will extend from randomization (Arm A and Arm B) or first dose of study drug (Arm C) until the End-of-Treatment Visit (which should occur 30 days from of last dose of study drug or prior to the start of a new anticancer treatment). Initiation of study treatment should occur within 72 hours of randomization. All subjects in Arms A and B will receive intravenous rituximab weekly for 4 consecutive weeks, followed by a second course of rituximab administered weekly for 4 consecutive weeks after a 3-month interval. In addition, all subjects in Arms A and B, according to randomization, will receive oral study drug (ibrutinib or matching placebo), administered daily and continuously until criteria for permanent discontinuation of study drug are met ([Section 9.2](#)), such as IRC confirmed disease progression, study drug is no longer tolerable by subject, or study end. All subjects in Arm C will receive oral ibrutinib daily

and continuously until criteria for permanent discontinuation of study drug are met. Further information on dosing is provided in [Section 5](#). Efficacy evaluations will be performed as specified in [Section 7.5](#). Subjects with IRC confirmed progressive disease must discontinue all study treatment and may be assessed for potential cross over treatment.

[figure not shown]
After the End-of-Treatment Visit (30 days \pm 3 days from last dose of study drug or prior to the start of a new anticancer treatment) has been performed, subjects will continue to be monitored through either response follow-up or survival follow-up and will continue until death, lost to follow-up, consent withdrawal, or study end, whichever occurs first.

- The Response Follow-up Phase will occur for subjects who discontinue for reasons other than disease progression and will include efficacy assessments every 12 weeks until disease progression confirmed by an independent review committee (IRC), regardless of initiation of subsequent anticancer treatment. Subjects with IRC confirmed disease progression during the Response Follow-up Phase will continue to be followed in the Survival Follow-Up Phase.
- The Survival Follow-up Phase will occur for subjects with IRC confirmed disease progression and will be followed for survival, subsequent anti-cancer therapy and other malignancies every 12 weeks until study end.

Access to next-line ibrutinib (cross-over) for subjects with IRC confirmed disease progression and treated with placebo in combination with rituximab (Arm B) may be provided as outlined in [Section 7.7](#).

An independent Data Monitoring Committee (DMC) will be formed and constituted according to regulatory agency guidelines. Detailed information regarding the composition of the DMC and detailed DMC procedures will be provided in a separate charter. The DMC will review the safety data periodically and the interim analysis results and provide recommendations according to the charter.

3.1.1. Study Schema

3.1.2. Study Population

Subjects with untreated or previously treated WM will be evaluated in this study.

Eligible subjects must have a centrally confirmed clinicopathological diagnosis of WM as defined by consensus panel of the Second International Workshop on WM (Owen 2003); and must be in need of treatment in accordance with the “Consensus Panel Two” recommendations from the Second International Workshop on Waldenström’s Macroglobulinemia (Kyle 2003). Those subjects who have been previously treated must have documented relapsed/refractory disease to their most recent prior therapy.

Subjects in Arms A and B who had previously received a rituximab-containing regimen should have a documented response (at least MR) on the last prior rituximab-containing regimen and any previous rituximab therapy must have ended at least 12 months prior to enrollment in this protocol. Subjects who do not meet these rituximab-related criteria may be eligible to enroll in the open-label ibrutinib monotherapy substudy (Arm C).

3.2. Study Rationale

This is a randomized, double-blind, Phase 3 study designed to assess the safety and efficacy of ibrutinib in combination with rituximab compared to placebo in combination with rituximab in subjects with WM.

Rituximab, given either as a single agent or in combination, is currently a recommended therapy for previously treated and untreated WM in NCCN 2012 and ESMO 2013 guidelines (Anderson 2012; Buske 2013). All subjects will receive rituximab therapy; the study will include two treatment arms with approximately 75 subjects in both treatment arms to observe 71 PFS events. Assuming a 2-fold improvement (hazard ratio of 0.5) in median PFS of the rituximab in combination with ibrutinib arm over rituximab and placebo arm (median PFS assumption for rituximab and placebo arm is 15 months), the study has at least 80% power to achieve a statistical significance level of 5% (2-sided) under exponential distribution for PFS.

The proposed dose for rituximab is 375 mg/m² intravenous (IV) administered once weekly for 4 weeks followed by a second four-weekly rituximab course after a three-month interval. This dose was given in two single-arm published studies and provided the most current treatment guidance for rituximab in relapsed/refractory WM (Dimopoulos 2002a; Treon 2005).

The proposed dose for ibrutinib is 420 mg per day (3 x 140-mg capsules) administered once daily without interruption. In the ongoing Phase 2 study (NCT01614821), the 420 mg dose administered once daily demonstrated a favorable benefit/risk profile in subjects with previously treated WM as outlined in Section 1.6.2.

Ibrutinib at 420 mg in combination with rituximab 375 mg/m² intravenous (IV) has been shown to be a safe, well tolerated and an active treatment regimen in high-risk CLL subjects (Burger 2014). At a median follow up of 16.8 months, 31 of 40 subjects continued on therapy (14 out of 20 with del17p or TP53 mutation) without disease progression. 39 subjects were evaluable for response assessment per 2008 IWCLL guidelines; 34 (87%) achieved partial remission (PR), and three (8%) complete remission (CR), accounting for an ORR of 95%. The ORR in the 20 patients with del17p or TP53 mutation was 90% (16 PR, 2 CR). Among the 9 subjects that came off study, four subjects came off study because of possibly treatment-related toxicity (two pneumonia, one pulmonary infection and one grade 3 mucositis), three subjects had progressive disease (including one Richter's transformation), and two subjects died while on therapy unrelated to study treatment (one due to infectious complications and one due to respiratory and cardiovascular failure while in remission). Treatment generally was well tolerated, with infectious complications (8 cases of pneumonia and 9 cases of upper respiratory infections) being the most common complication. There were nine Grade 3 or higher, possibly related AEs: lung infection (n=2), neutropenia (n=2), upper respiratory infection (n=1), transaminase increase (n=1), mucositis (n=1), and peripheral neuropathy (n=1). Milder toxicities included Grade 1-2 bruising and rash (n=15), nausea or acid reflux (n=10), Grade 2 subdural hematoma (n=1), fatigue (n=7), bone pain, myalgias, and arthralgia (n=13), or diarrhea (n=17).

Taken together, these data support the utility of the proposed combination of rituximab and ibrutinib in subjects with WM.

Ibrutinib monotherapy has indicated favorable responses in subjects who failed prior CD20 therapy alone or in combination with other agents based on the findings in an ongoing Phase 2 study in WM (NCT01614821, refer to Section 1.6.2). Therefore, subjects who are considered refractory to the last prior rituximab-containing therapy may be eligible to enroll in the open-label monotherapy substudy (Treatment Arm C).

3.3. Statement of Compliance

This study will be conducted in compliance with this protocol, principles of International Conference on Harmonisation (ICH), Good Clinical Practice (GCP), Declaration of Helsinki, and all applicable national and local regulations governing clinical studies.

4. SUBJECT SELECTION

4.1. Eligibility Criteria for the Randomized Study (Arm A and Arm B)

4.1.1. Inclusion Criteria

To be enrolled in the study, each potential subject must satisfy all of the following inclusion criteria.

Disease Related

1. Subjects with untreated or previously treated Waldenström's Macroglobulinemia
 - a. Previously treated subjects must have either documented disease progression or had no response (stable disease) to the most recent treatment regimen.
2. Centrally confirmed clinicopathological diagnosis of WM in accordance with the consensus panel of the Second International Workshop on WM (Owen 2003).
3. Measurable disease defined as serum monoclonal IgM >0.5 g/dL.
4. Symptomatic disease meeting at least 1 of the recommendations from the Second International Workshop on Waldenström Macroglobulinemia for requiring treatment (Kyle 2003):
 - a. Constitutional symptoms documented in the subject's chart with supportive objective measures, as appropriate, defined as one or more of the following disease-related symptoms or signs:
 - i. Unintentional weight loss $\geq 10\%$ within the previous 6 months prior to Screening
 - ii. Fevers higher than 100.5°F or 38.0°C for 2 or more weeks prior to Screening without evidence of infection
 - iii. Night sweats for more than 1 month prior to Screening without evidence of infection
 - b. Clinically relevant fatigue which is not relieved by rest due to WM
 - c. Symptomatic hyperviscosity or serum viscosity levels greater than 4.0 centipoises
 - d. Lymphadenopathy which is either symptomatic or bulky (≥ 5 cm in maximum diameter)
 - e. Symptomatic hepatomegaly and/or splenomegaly and/or organ tissue infiltration
 - f. Peripheral neuropathy due to WM
 - g. Symptomatic cryoglobulinemia
 - h. Cold agglutinin anemia
 - i. IgM related immune hemolytic anemia and/or thrombocytopenia
 - j. Nephropathy related to WM
 - k. Amyloidosis related to WM
 - l. Hemoglobin ≤ 10 g/dL
 - m. Platelet count $< 100 \times 10^9$ /L
 - n. Serum monoclonal protein > 5 g/dL, with or without overt clinical symptoms

Laboratory

5. Adequate hematologic function defined as:
 - a. Absolute neutrophil count >750 cells/mm³ (0.75×10^9 /L) independent of growth factor support within 7 days of the first dose with study drug.
 - b. Platelet count $>50,000$ cells/mm³ (50×10^9 /L) without transfusion support within 7 days of the first dose of study drug.
 - c. Hemoglobin ≥ 8 g/dL without transfusion or growth factor support within 7 days of the first dose of study drug.
6. Adequate hepatic and renal function defined as:
 - a. Serum aspartate transaminase (AST) or alanine transaminase (ALT) <3.0 x upper limit of normal (ULN).
 - b. Estimated Creatinine Clearance ≥ 30 mL/min).
 - c. Bilirubin ≤ 1.5 x ULN (unless bilirubin rise is due to Gilbert's syndrome or of non-hepatic origin).
7. PT/INR ≤ 1.5 x ULN and PTT (aPTT) ≤ 1.5 x ULN unless abnormality is unrelated to a coagulopathy or bleeding disorder (when treated with warfarin or other vitamin K antagonists, then INR ≤ 3.0).

Demographic

8. Men and women ≥ 18 years of age.
9. Eastern Cooperative Oncology Group (ECOG) performance status of ≤ 2 .

Ethical/Other

10. Female subjects who are of non-reproductive potential (ie, post-menopausal by history - no menses for ≥ 2 year; OR history of hysterectomy; OR history of bilateral tubal ligation; OR history of bilateral oophorectomy). Female subjects of reproductive potential must have a negative pregnancy test upon study entry.
11. Male and female subjects of reproductive potential who agree to use highly effective methods of birth control (eg, condoms, implants, injectables, combined oral contraceptives, some intrauterine devices [IUDs], complete abstinence^a, or sterilized partner) during the period of therapy and for 30 days after the last dose of study drug and 90 days (males) after the last dose of study drug.

^a Complete abstinence is a highly effective method only if defined as refraining from heterosexual intercourse during the entire period of risk associated with the study treatments. The reliability of sexual abstinence needs to be evaluated in relation to the duration of the clinical trial and the preferred and usual lifestyle of the subject. http://www.hma.eu/fileadmin/dateien/Human_Medicines/01_About_HMA/Working_Groups/CTFG/2014_09_HMA_CTFG_Contraception.pdf

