5.2.1. Treatment Arm A (Ibrutinib/Rituximab)

Ibrutinib: 420 mg (3 capsules) orally administered daily beginning from Day 1 in Week 1
Rituximab: 375 mg/m² IV per package insert weekly for four consecutive weeks, followed by a second four-weekly rituximab course after a three-month interval.
Day 1 of Weeks 1-4 and Weeks 17-20 (total of 8 infusions of rituximab)

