5.3. Study Medication

5.3.1. Ibrutinib/Placebo

For the purposes of this study, ibrutinib and placebo refers to the blinded label study drug used in this study in treatment arms A and B. All subjects will follow the guidelines for ibrutinib dosing and toxicity management. Study drug refers to both ibrutinib and placebo. In the substudy (Arm C), subjects will receive ibrutinib and will also follow the guidelines for ibrutinib dosing and toxicity management.

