11.3.5. Pregnancy

Before study enrollment, subjects must agree to take appropriate measures to avoid pregnancy including the use of contraception or complete abstinence in accordance with the local approved rituximab label and ibrutinib guidance. However, should a pregnancy occur in a female study subject, consent to provide follow-up information regarding the outcome of the pregnancy and the health of the infant until 30 days old will be requested.

A female subject must immediately inform the Investigator if she becomes pregnant from the time of consent to 30 days after the last dose of ibrutinib/placebo or 18 months after the last dose of rituximab, whichever occurs later. A male subject must immediately inform the Investigator if his partner becomes pregnant from the time of consent to 90 days after the last dose of ibrutinib/placebo or 18 months after the last dose of rituximab, whichever occurs later. Any female subjects receiving study drug(s) who become pregnant must immediately discontinue study drug. The Investigator should counsel the subject, discussing any risks of continuing the pregnancy and any possible effects on the fetus.

Although pregnancy itself is not regarded as an adverse event, the outcome will need to be documented. Any pregnancy occurring in a subject from the time of consent to 30 days after the last dose of ibrutinib/placebo or 18 months after the last dose of rituximab, whichever occurs later, must be reported. Any pregnancy occurring in a subject's partner from the time of consent to 90 days after the last dose of ibrutinib/placebo or 18 months after the last dose of rituximab, whichever occurs later, must be reported. Any occurrence of pregnancy must be recorded on the Pregnancy Report Form Part I and sent via email or fax to Pharmacyclics Drug Safety, or designee, within 24 hours of learning of the event. All pregnancies will be followed for outcome, which is defined as elective termination of the pregnancy, miscarriage, or delivery of the fetus. For pregnancies with an outcome of live birth, the newborn infant will be followed until 30 days old by completing the Pregnancy Report Form Part II. Any congenital anomaly/birth defect noted in the infant must be reported as a serious adverse event.

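### The eligibility contraception period counts only from ibrutinib/placebo, while the pregnancy section ties contraception to the rituximab label and reporting to 18 months after rituximab; the passages need reconciling

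*Protocol*

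**What the plan says.** Two parts of the Protocol deal with avoiding pregnancy after treatment.

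- **Eligibility.** Section 4.1.1, criterion 11, has men and women of reproductive potential agree to highly effective birth control during therapy and "for 30 days after the last dose of study drug and 90 days (males) after the last dose of study drug". Section 7.7.1, criterion 9, repeats this for next-line ibrutinib. Section 5.3.1 says "Study drug refers to both ibrutinib and placebo", so these periods run from the oral drug. Rituximab is not named in either criterion.
- **Pregnancy.** Section 11.3.5 has subjects agree, before enrollment, to measures against pregnancy "including the use of contraception or complete abstinence in accordance with the local approved rituximab label and ibrutinib guidance". It gives no duration for that duty. It then sets the period for notifying and reporting a pregnancy. For a female subject this runs to "30 days after the last dose of ibrutinib/placebo or 18 months after the last dose of rituximab, whichever occurs later". For the partner of a male subject it runs to "90 days after the last dose of ibrutinib/placebo or 18 months after the last dose of rituximab, whichever occurs later".

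The oral drug is "administered daily and continuously until criteria for permanent discontinuation of study drug" are met (Section 3.1). Sections 5.2.1 and 5.2.2 place the eighth and last rituximab infusion on Day 1 of Week 20.

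**The concern.** One section gives exact contraception periods that leave rituximab out. Another brings rituximab in, by reference to a label and without a number. Neither refers to the other. Section 7.1.2 has sites document the Section 4 criteria to confirm eligibility, so the explicit 30-day and 90-day figures are the ones most likely to be applied.

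At stake is whether subjects and sites receive one consistent instruction on reproductive safety. A subject in Arm A or B who stops the oral drug early could finish the period in criterion 11 while pregnancies must still be reported because of rituximab. Scheduled pregnancy tests are at Screening and Day 1 only, unless local authorities require more (Section 7.2.8, Appendix 1). Later detection therefore depends largely on the subject knowing which period applies. No endpoint or analysis is affected.

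**Working it through.** The documents state no figure for the difference, so there is none to reproduce. The check compares the texts and then does date arithmetic.

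**Inputs**
- Last planned rituximab dose: Week 20 Day 1 (Sections 5.2.1, 5.2.2), which is study day 1 + 19 × 7 = 134.
- Reporting limit from rituximab: 18 months (Section 11.3.5), which is 18 × 365.25/12 = 547.9 days.
- Period in criterion 11 after the last oral dose: 30 days for women, 90 days for men.
- One month is taken as 365.25/12 = 30.44 days.

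**When the rituximab-based reporting window ends**
134 + 547.9 = day 681.9, about week 97.

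**When criterion 11 ends before it**
The two limits differ if the last oral dose falls before day 681.9 minus the period in criterion 11.
- Women: 681.9 − 30 = day 651.9, about week 93, or 651.9/30.44 = 21.4 months.
- Men: 681.9 − 90 = day 591.9, about week 85, or 591.9/30.44 = 19.4 months.

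For a subject who stays on oral drug past these points, criterion 11 runs at least as long as the reporting window.

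**Size of the difference**
Difference = 681.9 − (day of last oral dose + 30 or 90).
- Oral drug stopped on the day of the last planned infusion (day 134): women 681.9 − 164 = 517.9 days, about 17 months; men 681.9 − 224 = 457.9 days, about 15 months. These are the largest values, provided oral drug is not stopped before rituximab.
- Oral drug stopped at 15 months (day 456.6), the control-arm median PFS assumed in Section 10.5: women 681.9 − 486.6 = 195.3 days; men 681.9 − 546.6 = 135.3 days.

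**Who is outside this**
- Arm C receives no rituximab on study.
- Arm B subjects who start next-line ibrutinib come under criterion 9 of Section 7.7.1, which runs through that therapy plus 30 or 90 days. This can shorten or close the difference.

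**The case against.** **The rituximab label is already invoked.** A reader might infer that the time between the two limits carries no contraception requirement. Section 11.3.5 does not support that: it asks for agreement before enrollment to contraception in line with the local rituximab label. The footnote to criterion 11 also describes abstinence as "refraining from heterosexual intercourse during the entire period of risk associated with the study treatments", in the plural. This part of the objection stands, but it does not remove the inconsistency. The duty in Section 11.3.5 has no duration, sits outside the eligibility list, and may differ by country because the label is the local one. It also shows that rituximab was considered relevant to contraception, which makes its absence from the two criteria harder to explain.

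**The 18 months is a reporting window.** A reader might infer that the Protocol treats the whole 18 months as a period of risk, and hence that a fetal safety gap is shown. The documents do not say so. Section 11.3.5 uses 18 months only for notifying and reporting pregnancies, and the two kinds of period need not coincide. The label is not among the documents, so its contraception period cannot be compared with either figure. This stands.

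**Study drug might be read to include rituximab.** Section 5.3.1 says otherwise. Even on the looser reading, criterion 11 would give 30 or 90 days after rituximab, and the documents would still not show that this matches the label.

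**The number affected is unknown.** A reader might turn the design medians into a share of subjects: 1 − 0.5^(21.4/15) = 63% of Arm B and 1 − 0.5^(21.4/30) = 39% of Arm A with a PFS event before 21.4 months. Those are not shares of subjects affected. They count everyone regardless of reproductive potential, include deaths, equate a PFS event with stopping oral drug, leave out stops for toxicity or withdrawal, and ignore crossover ibrutinib. The documents give no basis for a better figure.

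**The consent wording cannot be seen.** Consent pages are not in the reviewed documents, so what subjects were told cannot be judged.

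**Conclusion.** The point holds as an internal inconsistency in the Protocol. Criterion 11 of Section 4.1.1 and criterion 9 of Section 7.7.1 state fixed periods that omit rituximab; Section 11.3.5 ties contraception to rituximab without stating a period.

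The inconsistency matters for Arm A and B subjects of reproductive potential whose oral drug stops before the 21.4-month (women) or 19.4-month (men) threshold. The 17-month and 15-month figures are extremes, for oral drug stopped on the day of the last infusion. All these figures assume that rituximab is given as scheduled and that no next-line ibrutinib follows. They measure the distance from criterion 11 to the reporting limit, not time shown to be without a contraception requirement. How many subjects are affected cannot be estimated from the documents.

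**What to change.** Reconcile criterion 11 of Section 4.1.1, criterion 9 of Section 7.7.1 and Section 11.3.5 so that the contraception requirement in relation to rituximab is stated consistently wherever it appears, with cross-references. Then check the consent text against the reconciled wording. This review does not say which period is right, nor that the contraception and reporting periods must be equal.

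The cost is a wording amendment and, if the check shows a mismatch, a consent revision. Sample size, endpoints and analyses do not change.
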